4.4. Safety monitoring

There are minimal risks related to the patient. Vitamin D treatment is a relatively safe procedure in properly selected individuals. There may be additional discomforts including close monitored by the research team in order to monitor the study and collect data. The risk and side effects for Vitamin D administration are minimal and discussed further in the drug description. We have outlined a detailed data and safety monitoring plan.

We have previously shown Vitamin D administration in our prospective, observational study for patients with Vitamin D levels <10ng/ml to be safe and without any adverse effect at dosages of 50,000 IU Qweek of ergocalciferol/vitamin D2. The dosages used in this study are comparable to other studies evaluating Vitamin D efficacy and safety (Bacon 2009, Von Restorff 2009, Amrein 2011, Amrein 2014). There was no reported adverse event from ergocalciferol/vitamin D2 administration during our prospective, observational trial along with recent trials evaluating cholecalciferol/vitamin D3.

For patient safety, we will continue daily monitoring of CBC, BMP, Calcium, Phosphate, and neurological examinations as per standard practice in the neurocritical care unit. Should risks be identified, modification of the protocol will be proposed. And should the trial prove unsafe, we plan to notify the IRB and terminate the study. The study principal investigator and co-investigators will be responsible for oversight of patient safety. In addition, an independent safety and data review committee of licensed physicians will evaluate the study data on a quarterly basis. Quarterly safety and data monitoring reports will be discussed among the investigators and safety committee. The study will remain double-blinded except in the case of possible safety issues warranting unblinding.

Participants will be withdrawn from the study should they demonstrate >grade 3 Common Terminology Criteria for Adverse Events (CTCAE) suggesting Severe or medically significant but not immediately life-threatening; hospitalization or prolongation of hospitalization indicated. In addition, patients will be withdrawn from the study should they show other signs/symptoms of vitamin D toxicity including, hypercalcemia, anorexia, nausea, vomiting, as well as polyuria, polydipsia, weakness, nervousness, pruritus, laboratory studies suggesting renal injury or failure (proteinuria, urinary casts, azotemia, metastatic renal calcifications). A checklist will be used to monitor patients. These findings can be uncovered by routine neurological and laboratory exams as per the ICU standard. Should adverse events be identified at higher or clustered rates than expected statistically, the trial will be modified or terminated.

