4.3. General protocol

1. Patients will be identified through primary treatment teams, including the Departments of Neurosurgery and Neurology, and through screening of the electronic medical record for patients admitted to the NCCU at the University of Utah Health Sciences Center. Patients admitted for non-elective indications as outlined in the inclusion criteria will be enrolled. The full inclusion and exclusion criteria are listed in Table 1. We expect most patients to be admitted to the neurosurgery service and NCCU.
2. A Vitamin D level will be drawn on all non-electively admitted NCCU patients as part of our standard admission protocol.
3. Patients with a Vitamin D level <20ng/ml, defined as deficient, will be consented for the trial. Patients that do not consent for the trial will be studied retrospectively as part of our standard-of-care similarly to our previous prospective trial. Women between 18-45 years of age will undergo a serum or urine pregnancy test to rule out pregnancy prior to enrollment.
4. Patients will be randomized 1:1 to receive Cholecalciferol (Vitamin D3, 540,000 IU once orally or by feeding) immediately or placebo by random number generator. Treatments will be blinded to the patient and physician care teams. Placebos will include similar tablets or liquid formulations that mimic the treatment drug but are indistinguishable.
5. A subsequent Vitamin D level will be drawn 3 days after drug administration or on date of discharge if sooner than 3 days to evaluate the adequacy of vitamin D repletion.
6. Primary outcomes will total hospital length-of-stay. Secondary outcomes will include in-hospital mortality, ICU length-of-stay, ICU complications (rates of sepsis/bacteremia, pneumonia, urinary tract infection), discharge Glasgow Outcome Score, medication adverse events, and quality-of-life metrics. Various patient demographic data will be acquired.
7. Subsequent 30-day mortality will be measured on standard clinical follow-up.

8. 1, 3 month and 6 month Glasgow Outcome Scores and quality-of-life metrics will be obtained. Physical therapy gait distance measurements as well as modified Rankin scale on discharge will be obtained.

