
• Name• Medical record number• Date of birth• Gender• Diagnosis• Ethnicity/race
Clinical Variables

• Date of admission to NCCU• Disease category (tumors, trauma, vascular, other)• Disease severity: Glasgow Coma Scale, Simplified Acute Physiology Score II• Medical comorbidities: diabetes, hypertension, heart disease, cancer history• Any surgeries during hospitalization• Randomization – vitamin D or placebo• Vitamin D level on admission• Date vitamin D level• Vitamin D level 3 days post treatment• Date vitamin D level 3 days post treatment• Date ICU discharge• Date hospital discharge• Date deceased• Glasgow Outcome Score on discharge• EQ-5D on discharge• Discharge disposition• Hospital complications (specifically: deep vein thrombosis, bacteremia, urinary tract infection, pneumonia, readmission to NCCU)• Glasgow Outcome Score at 3 and 6 months• EQ-5D at 1, 3 and 6 months• Physical therapy assessments at discharge• Modified Rankin Scale on discharge
Safety Monitoring

• Common Terminology Criteria for Adverse Events (CTAE) V4.0• Daily ICU laboratory studies (CBC, BMP, calcium, phosphate)• Daily neurological exam• Quarterly independent review of safety and data• Monitoring of adverse events

Table S1: Clinical Studies Evaluating Vitamin D in a Critical Care Environment			
Reference	Study type	Participants/ groups	Summary
Van den Berghe 2003	RCT	22 200 IU vs. 500IU	Minimal change in serum markers
Ostermann 2007	Retrospective cohort	100 Normal vs. insufficient vs. deficient	Hospital-free days were significantly different between patients with deficiency and sufficiency No significant relationship between 25(OH)D concentrations and mortality
Lucidarme 2010	Retrospective cohort	100 Normal vs. insufficient vs. deficient vs. undetectable	28-day mortality was significantly different between the four groups No significant association between 25(OH)D concentrations and length of ICU stay. 79% of patients had low 25(OH)D concentrations
Mata-Granados 2010	RCT	33 Placebo vs. 60,000 IU PO, vs. 2mcg IV vit D3	97% of critically ill patients were vitamin D deficient. Group B (60,000 IU) showed a statistically significant increase in 25(OH)D concentrations.
Cecchi 2011	Retrospective cohort	170 Severe sepsis vs. non-septic trauma	28-day mortality was not statically different between the two groups with rates of 27.9% in severe septic patients and 11.1% in trauma patients

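### No calcium, phosphate or BMP draw is specified after ICU transfer, and the one sample timed from the 540,000 IU dose measures vitamin D only

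*Combined protocol and SAP*

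**What the plan says.** Three statements give the source of the safety chemistry, and each refers to the ICU.

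- Section 4.4: "we will continue daily monitoring of CBC, BMP, Calcium, Phosphate, and neurological examinations as per standard practice in the neurocritical care unit".
- Section 4.4, after the list of toxicity signs: "These findings can be uncovered by routine neurological and laboratory exams as per the ICU standard".
- Table 2, under safety monitoring: "Daily ICU laboratory studies (CBC, BMP, calcium, phosphate".

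Table 1 differs slightly. Its data and safety monitoring row lists a daily review of the same laboratory values and does not mention the ICU. It gives no ward schedule and no duration.

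One sample is timed from the dose. Section 4.3 item 5 states: "A subsequent Vitamin D level will be drawn 3 days after drug administration or on date of discharge if sooner than 3 days". Its stated purpose is to check repletion, and vitamin D is its only analyte.

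The protocol also gives calcium a safety role. Section 4.2 excludes patients with hypercalcemia at entry. Section 4.8 describes the toxicity of high-dose vitamin D3 as minimal and mainly mild hypercalcemia. Section 4.4 states: "patients will be withdrawn from the study should they show other signs/symptoms of vitamin D toxicity including, hypercalcemia". The same list includes laboratory evidence of renal injury.

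**The concern.** Hypercalcemia and azotemia are found by blood tests. If those tests are specified only where ICU practice supplies them, the chance of finding either one depends partly on how long a patient stays in the ICU after the dose. A patient who moves to the ward soon after dosing may have little post-dose calcium data that the protocol itself requires. Even the day-3 draw, which does not depend on location, would not supply a value.

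What is at stake is how complete and even the safety data are. The withdrawal trigger, and the laboratory part of the medication adverse events listed as a secondary outcome, would be checked more thoroughly in some patients than in others. Table 2 names only ICU laboratory studies, so a calcium result obtained on the ward has no stated place in the dataset.

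**Working it through.** The plan gives no figure to reproduce. The check has two parts: a reading of every laboratory statement, and timing arithmetic.

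**Reading.** Sections 4.1 to 4.9, Table 1 and Table 2 contain no calcium, phosphate or BMP draw set for the ward, for discharge, for a fixed time after the dose, or for the 1, 3 or 6 month follow-up. The entry exclusion implies a calcium value before the dose, not after it.

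**Inputs.**
- Minimum expected ICU stay: 48 h (4.1).
- Latest randomization: 48 h after admission (4.2).
- Post-dose vitamin D draw: 3 days = 72 h after the dose (4.3 item 5).
- Planned patients: 218 per arm (4.9).

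**Assumptions.** ICU and hospital admission coincide, and the dose is given at randomization. T is the dosing hour after admission.

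**Reading A: the 48 h stay is counted from admission.** Post-dose ICU time = 48 − T. Day-3 draw at T + 72. Interval from ICU exit to draw = (T + 72) − 48 = T + 24.

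| T (h) | Post-dose ICU time (h) | Day-3 draw (h from admission) | ICU exit to draw (h) |
|---|---|---|---|
| 0 | 48 | 72 | 24 |
| 24 | 24 | 96 | 48 |
| 48 | 0 | 120 | 72 |

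**Reading B: 48 h of further stay is counted from enrolment.** Post-dose ICU time = 48 h. Interval to draw = 72 − 48 = 24 h.

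Under either reading, a patient with the minimum stay leaves the ICU before the day-3 draw. If hospital discharge comes before day 3, the draw moves to discharge and the interval is shorter.

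**ICU stay needed for the ICU panel to be running on post-dose day 3** (counted from admission) = 3 + T/24 days, which gives 3, 4 and 5 days for T = 0, 24 and 48.

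**Upper bound on added panels** = 2 × 218 = 436, one per patient. The number is lower wherever the daily panel already covers that day.

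The documents give total hospital stay for the site's earlier cohort but no ICU stay. The proportion of patients below these thresholds therefore cannot be derived.

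**The case against.** The strongest reply is that the plan may already cover the ward. Table 1's daily laboratory review carries no ICU label, and the wording in 4.4 can be read as naming the standard to follow rather than the point at which testing stops. This stands in part: the protocol nowhere says that testing ends at ICU transfer. But Table 1 describes review, not blood draws, and the statements that say where the tests come from all refer to the ICU. At best the plan is ambiguous.

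Second, 48 hours is a floor. Many patients may stay longer, and daily ICU testing is denser than a single timed sample. The 0-hour figure combines the shortest expected stay with the latest permitted randomization, so it is a corner case. This stands, and it limits the finding to patients who leave the ICU early.

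Third, other safeguards exist. Section 4.4 says "A checklist will be used to monitor patients", lists clinical signs, and adds that "an independent safety and data review committee of licensed physicians will evaluate the study data on a quarterly basis". These apply beyond the ICU panel, but none of them produces a calcium value, and the committee can review only what is collected.

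Fourth, the drug is given once, so a missed withdrawal trigger leaves no further dose to stop. Day 3 was chosen for repletion, and the documents give no time course for calcium. Both points are fair. The case for day 3 is that blood is already being drawn then, not that it is known to be the most informative day.

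A reader might also infer that the gap biases the comparison between arms. That would require treatment to change ICU stay, which the documents do not establish. The trial in Table S1 that began with the same dose reported no difference in mean hospital stay (19.3 vs. 20.1).

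**Conclusion.** The point holds as a gap in what is specified. No calcium, phosphate or BMP draw is set after ICU transfer, and the one dose-timed sample omits all three. At the minimum expected 48-hour ICU stay, clearly specified post-dose calcium coverage is at most 48 hours. It is shorter if dosing is later and the stay runs from admission. In each case it ends before a day-3 draw. These figures assume that ICU and hospital admission coincide and that dosing occurs at randomization.

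Two stronger conclusions are tempting and unsupported. The 24 to 72 hour intervals are not demonstrated gaps in testing, because ward teams may test and Table 1 may be meant to cover the whole stay. Nor do the documents show a serious hazard, since they expect mostly mild hypercalcemia. The share of patients affected is unknown. This is a cheap improvement to the completeness of safety data, and nothing here affects the primary outcome.

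**What to change.** Amend 4.3 item 5, 4.4 and Table 2 as follows.

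1. Add calcium, phosphate and BMP to the blood draw on day 3, or at discharge if sooner, on whatever ward the patient is, unless the daily panel already covers that day.
2. Record any ward calcium, phosphate and BMP results in the safety dataset.

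The cost is at most 436 added panels, possibly an extra tube at the same draw (the documents do not say whether the vitamin D specimen can serve these assays), some abstraction of ward results, and a few lines of protocol text.

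The limit is that laboratory ascertainment after day 3 would still depend on ward practice. Because the documents give no calcium time course, they offer no basis for choosing a later fixed laboratory day.

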4.8. Selection of therapeutic agent

Patients will be supplemented with cholecalciferol (vitamin D3) or placebo. Two major vitamin D compounds exist in humans, ergocalciferol (vitamin D2) and cholecalciferol (vitamin D3) and recent guidelines suggest that either vitamin D2 or vitamin D3 can be supplemented in patients with hypovitaminosis D (Holick 2011). One study evaluating short-term supplementation with vitamin D2 in an critical care setting demonstrate that only 26% of patients receiving 50,000 IU three times per week achieved normal vitamin D levels (Dickerson 2015). Critically ill patients have been suggested to have a blunted response to vitamin D supplementation. Nonetheless, a number of randomized trials have shown the ability of high dose vitamin D3 to adequately replete critically ill patients with minimal toxicity, mostly mild hypercalcemia (Quraishi 2015, Nair 2015, Amrein 2011, Amrein 2014). Intramuscular (200,000 IU) or oral (540,000 IU) have been shown to adequately replete vitamin D levels in the majority of patients by 2-7 days after treatment. For this reason we have chosen to supplement with cholecalciferol (540,000 IU orally).

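### Section 4.4 withdraws patients from the study after a single dose, with no rule for later follow-up or analysis; post-discharge GOS and EQ-5D are most exposed

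*Combined protocol and SAP*

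**What the plan says.** Section 4.4 has two withdrawal rules, and both take the patient out of the study, not only off treatment. The first reads "Participants will be withdrawn from the study should they demonstrate >grade 3 Common Terminology Criteria for Adverse Events (CTCAE" and describes the qualifying events partly as "hospitalization or prolongation of hospitalization indicated". The second reads "patients will be withdrawn from the study should they show other signs/symptoms of vitamin D toxicity including, hypercalcemia, anorexia, nausea, vomiting" and goes on to other symptoms and to laboratory signs of renal injury. The same section adds: "The study will remain double-blinded except in the case of possible safety issues warranting unblinding".

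Treatment is one administration (4.3 item 4: "540,000 IU once orally or by feeding"). Section 4.8 describes high-dose D3 as repleting critically ill patients "with minimal toxicity, mostly mild hypercalcemia".

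After dosing, 4.3 plans a repeat level ("A subsequent Vitamin D level will be drawn 3 days after drug administration", or at discharge if sooner), 30-day mortality from routine clinical follow-up, and GOS and quality of life at 1, 3 and 6 months. Table 2 lists EQ-5D at those three times and GOS at 3 and 6 months. It also lists hospital discharge date and date of death, with no exception for withdrawn patients.

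Section 4.9 gives a t-test and a multivariate regression for length of stay and a 10% dropout allowance. Neither 4.9 nor the statistical row of Table 1 names an analysis set. No passage says what happens to follow-up after withdrawal.

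**The concern.** With a single dose there is no later study dose for withdrawal to stop. What it can stop is participation: the day-3 level and the post-discharge assessments.

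The triggers are not neutral. One is described in terms of a longer hospital stay, which is the primary outcome. Another, hypercalcemia, is what 4.8 names as the main toxicity of the active drug. Care teams are blinded, which limits a difference between arms, but blinding cannot prevent a laboratory effect of the drug.

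Two things are at stake. GOS and EQ-5D after discharge need continued contact, so patients with severe events could drop out of those comparisons. For length of stay the data should exist, but nothing fixes in advance whether these patients are counted. The 10% allowance replaces numbers; it does not correct for selective loss.

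**Working it through.** **1. The plan's own figure on patient loss.** 198 × 1.10 = 217.8, so 218 per group and 436 in total, as 4.9 states. (Dividing instead, 198 / 0.90 = 220.) This figure is not in dispute.

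**2. SD of length of stay.** The plan states neither SD nor power, so both are back-solved.
- From 198 per group, 2 days, two-sided 0.05: SD = 2 × √(198/2) / (1.960 + z_power). At 80% power, 2 × 9.950 / 2.802 = 7.10 (7.09 with the t distribution). At 90%, 2 × 9.950 / 3.242 = 6.14.
- From the earlier observational study, 8.21 vs 6.36 days (difference 1.85), assuming the 203 and 321 given in section 2 for mortality are also the length-of-stay group sizes: √(1/203 + 1/321) = 0.0897. With p=0.002 (4.9), SE = 1.85/3.106 = 0.596 and SD = 6.64. With p=0.038 (section 2), SE = 1.85/2.080 = 0.889 and SD = 9.92.

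The two p-values belong to the same pair of means and imply different SDs. The value 6.64 lies inside 6.14 to 7.09. The value 9.9 is kept only as a high case; it would give 52% power at 198 per group.

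**3. Bias if withdrawn patients were left out.** Assumptions: no true effect; log-normal stay with mean 8.21 days; chance of being retained = exp(−h_b × LOS − h_e × min(LOS, w)). Here h_b is set to give the placebo withdrawal rate and h_e the active rate. The window w is 5 or 7 days (early excess) or the whole stay (extreme case). False benefit = retained placebo mean − retained active mean. The withdrawal rates are assumptions; the documents give none.

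Example, SD 7.09, 10% vs 20%, w = 7 days: 7.625 − 7.445 = 0.180 days.

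| Placebo vs active withdrawn | Early excess, SD 6.14–7.09 | Early excess, SD 9.9 | Whole stay, SD 6.14–7.09 | Whole stay, SD 9.9 |
|---|---|---|---|---|
| 2% vs 5% | 0.02–0.05 d | 0.05–0.08 d | 0.14–0.18 d | 0.32 d |
| 10% vs 15% | 0.04–0.09 d | 0.09–0.14 d | 0.22–0.28 d | 0.43 d |
| 10% vs 20% | 0.08–0.18 d | 0.19–0.28 d | 0.44–0.55 d | 0.83 d |

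Equal rates give 0. With 10% on placebo and 5% on active over the whole stay, the bias is 0.22 to 0.48 days against vitamin D.

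**4. Type I error.** 20,000 simulated trials per case, 218 randomised per arm, pooled t-test, withdrawn patients dropped, across all three SDs. For the three rate pairs in order:
- Early excess: 4.6% to 5.4%, 4.9% to 5.3%, 5.1% to 6.2%.
- Whole stay: 5.3% to 6.3%, 6.4% to 8.8%, 12% to 20%.
- All randomised patients analysed: 4.4% to 5.4% in every case.

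**5. Power with equal withdrawal.** At SD 7.09, 218 per arm gives 83.6% for 2 days. Leaving out 20% (174 remain) or 30% (153 remain) per arm gives about 75% or 69%.

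No size is computed for GOS or EQ-5D, because the documents give no basis for one.

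**The case against.** The strongest reply is that withdrawal from the study is not omission from the analysis, and that the surrounding text points towards inclusion. Discharge and death dates are listed without exception. Medication adverse events are a secondary outcome, which could not be reported if these patients were dropped. Even people who decline consent are covered from records: "Patients that do not consent for the trial will be studied retrospectively as part of our standard-of-care". This stands for length of stay and mortality. A reader might infer that the plan excludes withdrawn patients from the primary comparison, or loses their length of stay; the documents support neither. But data that can be recovered still need a rule that they will be used, and the argument does not protect GOS and EQ-5D after discharge.

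A reader might also infer that the primary result would be seriously biased. The 12% to 20% type I error requires both a doubling of withdrawals on active drug and a drug-related excess lasting the whole stay. Neither has support: 4.4 reports no adverse events in the earlier study, 4.8 reports minimal toxicity, and an excess in the first days suits a single dose better. The symptom list is also framed as signs of vitamin D toxicity, so not every episode of nausea need trigger it.

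Finally, the direction is assumed. The model makes withdrawal more likely in longer stays, whereas severe events may also precede early death, which shortens stay. That stands as a limit on the calculation.

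**Conclusion.** The point holds as a rule that, followed as written, ends participation after randomisation for reasons tied to outcome and possibly to arm, while stopping no study treatment. The firm consequences are possible loss of post-discharge GOS and EQ-5D, and an open choice of who enters the length-of-stay comparison.

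For length of stay the likely size is small: 0.02 to 0.18 days at SD 6.14 to 7.09 and at most 0.28 days at SD 9.9, with type I error about 5% to 6.5% allowing for simulation error. This is conditional on an exclusion the plan never states, on assumed withdrawal rates, and on withdrawal being more frequent on vitamin D and in longer stays. It should be fixed because the choice is otherwise left until after results are seen. Confidence is moderate.

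**What to change.** Leave the event criteria and all care decisions unchanged.

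- In 4.4, state that patients who meet a criterion stay in follow-up for discharge date, death, GOS and EQ-5D unless consent is withdrawn.
- In 4.4, reconcile the threshold of above grade 3 with the description beside it of events that are severe but not immediately life-threatening, which reads as grade 3 itself. Which is meant is for the investigators to settle.
- In 4.9, state that the primary analysis includes every randomised patient in the assigned arm, and that criterion-meeting events are reported by arm.

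The cost is a few sentences and a little more collection of GOS and EQ-5D after discharge. Discharge and death dates are already planned in Table 2.
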